5.4 Physical Examinations

Physical examination results (abnormalities only) at each study visit will be listed.

5.5 Concomitant Medication

Pre-treatment and concomitant medication administered during the study will be listed. Concomitant medications will be coded using the WHODRUG Dictionary. Medications initiated prior to start of treatment and maintained during the study, or taken during the course of the study will be considered as concomitant medications. Medications administered prior to and not continuing on the study treatment will be considered as prior medications. Medications with partial or missing start date will be assumed to be concomitant medications, unless there is clear evidence (through comparison of partial dates or end date with the date of tipifarnib treatment) to suggest that the medications are not taken during study.

5.6 Vital Signs

Individual vital sign measurements will be listed by treatment and summarized using descriptive statistics. Summary statistics will also be provided for change from baseline in vital sign

measurements by treatment. Baseline value is defined as the Day 1 (randomization) measurement. If the Day 1 measurement is not available, the last non-missing pre-randomization measurement will be used as the baseline value.

5.7 Clinical Laboratory Values

Individual lab values will be listed by treatment and visit, and summarized using descriptive statistics. Summary statistics will also be provided for change from baseline in lab values. Shift tables from baseline to last double-blind visit will also be produced for the laboratory assessments based on the categories of Low, Normal, and High. Baseline value is defined as the Day 1 (randomization) measurement. If the Day 1 measurement is not available, the last non-missing pre-randomization measurement will be used as the baseline value. Standard units (SI) will be used to report results in listings and tables.

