Study Design:	The study will be conducted as a placebo-controlled, randomized (2:1, APD811:placebo), 22 week double-blind study which will include a dose titration period of up to 9 weeks. An additional transition period of 3 weeks (±1 week) will occur for those patients who elect to enroll into the open-label extension study, APD811-007. Patients that do not continue in the extension study will have a 3-week follow-up visit. Approximately 60 patients with PAH will be enrolled.			
	Safety will be assessed by the Safety Monitoring Committee (SMC). The SMC will review safety data including adverse events, blood pressure and heart rate periodically, in order to ensure patient safety and determine an appropriate dose titration regimen.			

To be eligible to enroll in the extension study APD811-007, patients must complete study APD811-003. Additionally, placebo treated patients who discontinue study drug treatment due to clinical worsening in APD811-003 will be permitted to enroll in APD811-007, upon approval of the medical monitor, provided that all end of study procedures including right heart catheterization are performed per protocol.

Patients will be receiving concomitant oral disease-specific PAH therapy consisting of an endothelin receptor antagonist (ERA) and/or an agent acting on the nitric oxide pathway, a PDE5 inhibitor or a soluble guanlyate cyclase stimulator, provided the dose has remained stable for at least 3 months prior to the start of Screening. Patients should continue the same dose and regimen of these medications for the duration of the study.

The use of the following therapies, which may affect PAH, are permitted:

- Vasodilators (including calcium channel blockers), digoxin, spironolactone, or L-Arginine supplementation; if on a stable dose for at least 1 month prior to the start of Screening and should remain unchanged during the study.
  - Doses of spironolactone and digoxin may be held or reduced as necessary to protect the patient's safety. Doses may not be increased in the month before Day 1 and during the controlled study.
- Diuretics may be dosed as clinically indicated throughout the study.
- Intravenous inotropes within 1 month of starting Screening are not permitted.

In an attempt to maintain balance across treatment groups, the following stratification factor will be utilized during patient randomization:

• Baseline WHO/NYHA Functional Class (Class II vs. III or IV)

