Study drug administration h,i	→ j						
Six-minute walk test k	X	X	X	X	X		
Right heart catheterization				X l			

<sup>a Reference to pre-dose and post-dose activities in this schedule apply to the morning dose of study drug.

For patients who terminate early from the study and is unable to return for the follow-up visit at Week 25, AE and concomitant medication follow-up may be conducted by telephone.

<sup>c Patients should have all assessments including RHC, 6MWT and BNP/NT-proBNP completed prior to entering the transition period.

d Safety ECGs should be completed **pre-dose**.

<sup>e Clinical laboratory tests will include hematology, serum chemistry, coagulation, and urinalysis. Clinical laboratory tests will be completed **pre-dose**.

Serum pregnancy test will be completed **pre-dose** at each visit during the treatment period.

Vital sign measurements (blood pressure, heart rate, respirations, body temperature, and pulse oximetry, taken in supine position after 5-minute rest) will be taken **pre-dose**.

<sup>h Study drug should be taken with food.

On days with scheduled study visits, patients should **not** take their morning dose of study medication at home in order to complete pre-dose study procedures.

Patients entering the APD811-007 study will remain on current dose through the transition period. Patients who do not continue into the APD811-007 study will discontinue study medication at Week 22 visit but not prior to undergoing the final RHC, and will return for follow-up visit at Week 25; if the patient is unable return for the follow-up visit, AE and concomitant medication follow-up may be conducted by telephone.

<sup>k 6MWT should be completed **pre-dose** at approximately the same time of day at each designated visit.

			Transition Period			
Evaluation a		Treatment Period	End of Study (EOS) Visit	Follow-up Visit (start of OLE) ±1 week b		
Study Week	10	14	18	22 c	25	
Day	70	98	126	154	175	
BNP/NT-proBNP m	X			X	X	
Pharmacokinetic blood sample n	X	X	X	X		
WHO/NYHA functional class assessment o	X	X	X	X	X	
Assessment of clinical worsening	X	X	X	X	X	
Adverse event monitoring	+					
Concomitant medication monitoring	+				—	

RHC will be performed as part of Week 22 end-of-study procedures.

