## 5.6.2 Study Transition Period

At the end of the treatment period and after all Week 22 study assessments are performed, patients who are eligible and who elect to enroll in the APD811-007 study, will continue current treatment through the 3 week (±1 week) follow-up visit (Week 25). During this 3-week (±1 week) period, the individual patient database will be locked allowing for

subsequent unblinding of the individual patient and enrollment into the APD811-007 OLE. The Week 25 visit will serve as the baseline visit for the APD811-007 OLE study.

For patients who do not enter the extension study, study drug is stopped after the treatment period at the Week 22, End of Study Visit.

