#### 7.4.3.2 Week 25\* Follow-up Visit (±1 week)

Following a 3 week ( $\pm 1$  week) transition period, the following assessments will be done:

- Physical exam
- Safety ECG
- Clinical laboratory tests (to include hematology, coagulation parameters [PT/PTT, INR], serum chemistry, and urinalysis)
- Serum hCG pregnancy test (females only)
- Vital signs
- Study drug administration (current dose) for patients continuing into the APD811-007 OLE study
- 6MWT
- BNP/NT-proBNP pre-dose according to Table 2
- Assessment of clinical worsening
- WHO/NYHA functional class assessment
- Record adverse events
- Record concomitant medications

\*If appropriate, patients will 'switch' to the long-term open label extension study (APD811-007), thus Week 25 will also serve as the baseline visit for the APD811-007 OLE study.

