8.3 Description of Data Handling Procedures Prior to Unblinding

All data will be screened, reviewed, and declared clean before data are unblinded according to Novella (Data Management CRO) guidelines and standard operating procedures. At the end of the treatment period and after all Week 22 study assessments are performed, patients who are eligible and who elect to enroll in the APD811-007 study, will continue current treatment through the 3 week (± 1 week) follow-up visit (Week 25). During this 3 week (± 1 week) period, the individual patient database will be locked allowing for subsequent unblinding of the individual patient and enrollment into the APD811-007 OLE Study. For patients who do not enter the extension study, study drug will be stopped after the treatment period at the Week 22, End of Study Visit and their individual patient database will not be locked, frozen or unblinded until the end of the study.

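### The only laboratory shift table runs from baseline to a single, undefined last visit, so an on-treatment abnormality that has resolved by then counts as no shift

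*SAP*

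**What the plan says.** SAP 5.7 states: "Shift tables from baseline to last double-blind visit will also be produced for the laboratory assessments", in the categories Low, Normal and High. Protocol 9.5.3.5 uses the same rule. Neither document defines the last double-blind visit. Neither plans a shift to the worst value, a shift by visit, or a count of patients with any post-baseline abnormality.

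SAP 5.7 also provides listings of individual values by treatment and visit, descriptive statistics, and change from baseline. Protocol 9.5.3.5 allows a clinically significant change to be recorded as an adverse event (AE) if the investigator or sponsor thinks it appropriate.

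The design text bears on which visit is meant:

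- The Protocol synopsis describes a "22 week double-blind study which will include a dose titration period of up to 9 weeks" and adds: "Patients that do not continue in the extension study will have a 3-week follow-up visit".
- For patients not entering the extension, Protocol 5.6.2 says that "study drug is stopped after the treatment period at the Week 22, End of Study Visit". The footnotes to Protocol Table 2 say that they "discontinue study medication at Week 22 visit but not prior to undergoing the final RHC".
- Laboratory tests are repeated at the Week 25 follow-up (Protocol 7.4.3.2).
- SAP 8.3 says of patients who do not extend that "their individual patient database will not be locked, frozen or unblinded until the end of the study".

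**The concern.** A baseline-to-last shift table shows a patient's state at the end. It does not show whether the patient was ever abnormal on drug. Under Protocol 5.6.1 the dose may be lowered for safety reasons at any time, and under 6.15 a patient may be withdrawn for an intolerable AE. A reversible laboratory effect may therefore have gone by the last sample, and the table then reads Normal to Normal.

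The undefined end visit adds a second problem. If a programmer took an off-drug sample as the last visit, recovery after stopping would also be tabulated as no shift.

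Safety and tolerability is a secondary objective in Protocol 2.2 and a separate safety objective in SAP 1.2.3. What is at stake is how well the laboratory tables describe reversible effects. No efficacy conclusion depends on this.

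**Working it through.** The documents give no figure for this table, so there is none to reproduce. The check has three steps.

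**1. Samples available and samples used.** Protocol Table 1 schedules post-baseline laboratory tests at Weeks 2, 5 and 9. Table 2 adds Weeks 10, 14, 18, 22 and 25. That is 3 + 4 = 7 on treatment, plus Week 25. The shift table uses one value per patient.

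**2. What a Week 22 table can show.** This is an illustration. Assume that each affected patient has one abnormal episode, with onset uniform over Weeks 0 to 22 and a fixed length of L weeks, and completes to Week 22.

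- Present at Week 22: probability L/22.
- Seen at one or more on-treatment samples: the total length of the union of the intervals from w − L to w (within 0 to 22), for w = 2, 5, 9, 10, 14, 18, 22, divided by 22.
- For L = 2 the union is 0–2, 3–5, 7–10, 12–14, 16–18 and 20–22, which is 13 weeks: 13/22 = 0.59. For L of 4 weeks or more the union covers all 22 weeks.

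| Assumed length (weeks) | Seen at any on-treatment sample | Present at Week 22 | Share of seen episodes in a Week 22 table |
|---|---|---|---|
| 2 | 0.59 | 2/22 = 0.09 | about 15% |
| 4 | 1.00 | 4/22 = 0.18 | about 18% |
| 8 | 1.00 | 8/22 = 0.36 | about 36% |
| 13 | 1.00 | 13/22 = 0.59 | about 59% |
| Lasting to Week 22 | 1.00 | 1.00 | 100% |

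The lengths are assumptions, because the documents give no information on laboratory episodes.

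**3. Which visit is last.** Three points favour Week 22 or early termination. The study is called a 22-week double-blind study, Table 2 labels Week 22 the End of Study visit, and it labels Week 25 a follow-up visit. On this reading a completer's value is on treatment, since laboratory samples are taken before the morning dose (Table 2) and drug is not stopped before the final catheterization. Early terminators have the full end-of-study safety evaluations (Protocol synopsis), which include laboratory tests (Protocol 7.4.3 and 7.4.3.1).

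Nothing in the text excludes an off-drug value:

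- Patients who do not extend are off drug at Week 25, are sampled there and are still blinded (SAP 8.3).
- The Week 22 window in SAP 8.2 Table 1 is any day after Day 140, with no upper limit, so Day 175 falls inside it. The closest-to-target rule would normally pick Day 154 for a completer, and the table is not expressly assigned to laboratory data.
- No maximum interval is given between the last dose and the termination sample. Protocol 6.9 mentions stopping drug first and the termination procedures second.

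If a Week 25 sample were used after a Week 22 stop, the interval is 3 weeks ± 1 week. With the half-life of 20.5 to 26.4 hours in Protocol 1.1.3, 21 days is 504/26.4 = 19 to 504/20.5 = 25 half-lives. For 14 days the range is 13 to 16, and for 28 days 25 to 33. Drug would be washed out, and any abnormality that recovers on stopping would be absent.

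**The case against.** The best reply is that the data are kept elsewhere. Every value is listed by treatment and visit, and with about 60 patients those listings can be read. An abnormal value stays in the summary of the visit where it was drawn, even if the patient leaves later. Protocol 6.13.1 includes abnormal laboratory findings in its definition of an AE, and 6.13.6.1 records dose reduction and withdrawal. SAP 5.2 counts patients with dose reductions, and SAP 5.3 tabulates AEs leading to discontinuation. A baseline-to-last shift is also a legitimate summary, applied alike to both arms, and no test depends on it. All of this stands. It rules out any claim that information is lost.

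These outputs do not replace the missing count. Means dilute one patient's excursion, and listings give no tally by arm. AE tables count only what was judged worth reporting, and Protocol 9.5.3.5 leaves that to discretion.

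A reader might also infer that Week 25 is the end visit, so that the table mixes on-drug and off-drug values. The documents do not support this as fact, because the wording favours Week 22 or early termination. For a patient who stops early, the termination visit is the natural endpoint, and Week 25 contact may be by telephone, without laboratory tests. Continued blinding does not settle the matter either. Patients entering the extension have their records locked for unblinding between Weeks 22 and 25, so on that criterion their Week 25 value is not clearly double-blind.

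**Conclusion.** The point holds as a gap in safety reporting. Whichever visit is meant, the only planned categorical laboratory table uses one value per patient out of seven scheduled on-treatment samples, and it cannot show an abnormality that resolved earlier. The 15% to 59% range rests on the assumed episode lengths and uniform onset. For abnormalities that last to Week 22 nothing is missed.

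The undefined end visit is an ambiguity to close and does not show that off-drug values will be used. A reader might infer that the table is biased in favour of APD811. The documents give no rate of laboratory abnormality, dose reduction or extension uptake by arm, so neither the direction nor the size of any distortion between arms can be stated. The planning allowance of up to 30% dropout before the repeat catheterization (0.30 × 60 = 18 patients) shows only that a fair number of table entries could come from termination visits.

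This is a cheap improvement. The primary analysis, alpha and sample size are unaffected.

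**What to change.** In SAP 5.7:

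1. Define the endpoint of the existing shift table as the last on-treatment value, and state how long after the last dose a sample still counts as on treatment.
2. Add shift tables from baseline to the lowest and, separately, to the highest on-treatment value. Include unscheduled samples and termination samples drawn on treatment.
3. Summarise Week 25 laboratory values separately for patients still on drug and patients who had stopped.

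The cost is SAP wording and a few extra tables from data already collected. The one drawback is that worst-value tables show more shifts in both arms, because each patient has several chances to be out of range. They must be read against placebo, and not as absolute rates.

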5.8 Safety ECGs

Individual safety ECG values will be listed by treatment and visit, and summarized using descriptive statistics. Intervals to be provided for each ECG are: RR, PR, QRS, QT, QTc, QTcB, and QTcF. Post-screening ECGs will be compared with the baseline ECG. Summary statistics will also be provided for change from baseline in ECG values. Baseline value is defined as the Day 1 (randomization) measurement. If the Day 1 measurement is not available, the last non-missing pre-randomization measurement will be used as the baseline value.

6 OTHER ANALYSES

6.1 Interim Analyses

No interim analyses are planned for this study.

6.2 Subgroup Analyses

Subgroup analyses for the efficacy endpoints (PVR, 6MWD and other exploratory parameters) will be performed in order to explore whether the treatment effects are consistent across different subgroups. The baseline patient characteristics below are the subgroup factors to be explored.

- Sex (Male vs. Female)
- Age: < vs. \geq median age, \geq vs. < 65 years
- Race (White vs. Non-white)
- Baseline WHO/NYHA Functional Class (Class II vs. III or IV)
- Class of PAH therapy at baseline (ERA, PDE5, sGC)
 - With ERA vs. without ERA
 - With PDE5 vs. without PDE5
 - With sGC vs. without sGC
 - Monotherapy ERA
 - Monotherapy PDE5
 - Combination therapy: ERA + PDE5
- Etiology: IPAH vs Other Conditions
- Baseline 6MWD: <380m vs. \geq 380m
- Baseline mean pulmonary arterial pressure (mmHg): < median vs. \geq median
- Baseline pulmonary vascular resistance: < median vs. \geq median
- Baseline pulmonary vascular resistance: \leq 400 vs. > 400 units
- Baseline pulmonary vascular resistance index: < median vs. \geq median
- Baseline BNP/NT-proBNP: < median vs. \geq median
- Location: (North America vs. “Rest of World (Europe & Australia)”)
- Time since PAH diagnosis: < median vs. \geq median

Due to the fact that this study is 1:2 randomization ratio and sample size for placebo group is approximately 20, there will be no inferential comparison between treatment groups within a subgroup of subjects. Instead, summary statistics (N, mean or median, SD, 95% CI for change or percent change from baseline or N, frequencies, proportions, and 95% CI) will be provided for each of the subgroups by treatment group. Between treatment group difference and 95% CI will be reported for each subgroup for illustration purpose. Additional subgroup analyses and/or revision of above subgroup definition may be specified after database lock to accommodate available data as appropriate.

6.3 Multiplicity

The principal evaluation of the efficacy of APD811 will be based on testing the primary hypotheses for PVR and 6MWD. The testing procedure specified in the Section 4.3 Approaches to Efficacy Analyses preserves the overall Type 1 error rate for testing the primary hypotheses. Note that testing for secondary and exploratory endpoints will proceed only if the comparison for the change from baseline in PVR is significant.

Comparisons involving other efficacy endpoints and time points are considered supportive or exploratory and will be made at $\alpha=0.050$ level (two-sided). No multiplicity adjustment will be made for these other comparisons.

6.4 Safety Monitoring Committee

The SMC will oversee the safe conduct of the trial, and in particular, guide dose titration in order to determine a suitable scheme to achieve the optimal dose within the 9-week titration period while maintaining patient safety. Based on review of safety and tolerability information, the SMC may recommend a higher starting dose, different dose increments and/or time at each dose before escalation (escalation scheme), different dosage strengths, and even a higher final dose level than 0.3 mg bid. The roles and responsibilities of the SMC will be outlined in a separate charter. The SMC will include the following members: at least 2 physicians, representing expertise in clinical care of patients with PAH, and expertise in drug development; and a biostatistician.

7 STATISTICAL TECHNICAL ISSUES

7.1 Planned Statistical Power and Sample Size

For the APD811 versus placebo comparison, 28 patients in the APD811 group and 14 patients in the placebo group will have 90% power to detect a between-treatment difference of 350 dyn·s·cm⁻⁵ in PVR. This calculation was based upon the pooled SD estimate of 320.3 dyn·s·cm⁻⁵ for the mean change from baseline in PVR at Week 17 observed in the selexipag phase 2 study.

Assuming that up to 30% of patients may drop out of the trial before a post-randomization repeat RHC is performed, 40 patients will be randomized to the APD811 group and 20 patients will be randomized to the placebo group. For 6MWD, 40 patients in APD811 group and 20 patients in the placebo group will have 80% power to detect a between-treatment difference of 50 meters in 6MWD assuming pooled SD estimate of 65 meters.

